14.3 Weeks 4, 8, 16, 20, 28, and 32 (\pm 5 days) Procedures/Assessments

- [REDACTED]
- [REDACTED]
- [REDACTED]
- C-SSRS.
- Telephone administered ALSFRS-R.
- Current medical condition review.
- Limited physical examination.

- Weight.
- Vital signs.
- Spirometry.
- Clinical laboratory tests.
- Urine pregnancy test.
- [REDACTED]
- [REDACTED]
- Subject diary review.
- Study drug accountability.
- Contact IXRS and dispense study drug kits.
- AEs and concomitant medications.

14.4 Week 12 and 24 (\pm 5 days) Procedures/Assessments

- [REDACTED]
- [REDACTED]
- [REDACTED]
- C-SSRS.
- Telephone administered ALSFRS-R.
- Investigator administered ALSFRS-R.
- [REDACTED]
- Current medical condition review.
- Limited physical examination.
- Weight.
- Vital signs.
- Spirometry.
- [REDACTED]
- Clinical laboratory tests.
- Lipid Panel.
- HbA1c.

- Urine pregnancy test.
- [REDACTED]
- [REDACTED]
- Subject diary review.
- Study drug accountability.
- Contact IXRS and dispense study drug kits.
- AEs and concomitant medications.

14.5 Week 36 (\pm 5 days)/Early Termination Procedures/Assessments

- [REDACTED]
- [REDACTED]
- [REDACTED]
- C-SSRS.
- Telephone administered ALSFRS-R.
- Investigator administered ALSFRS-R.
- [REDACTED]
- Current medical condition review.
- Complete physical examination.
- Weight.
- Vital signs.
- Spirometry.
- [REDACTED]
- Clinical laboratory tests.
- Lipid Panel.
- HbA1c.
- Serum pregnancy test.
- [REDACTED]
- Subject diary review.
- Study drug accountability.

- Contact IXRS and dispense study drug kits (for taper for subjects **not** entering the open label extension).
- AEs and concomitant medications.

Subjects who early terminate from the Randomized Treatment Period for any reason must undergo the taper of study drug (2x/week for 2 weeks followed by 1x/week for 1 week) and should complete the End of Taper and Follow-up Visits.

14.6 Week 36 (\pm 5 days) Additional Procedures/Assessments for Subjects Entering the Open Label Extension Only

- Open Label Extension entry criteria review.
- Contact IXRS and dispense active study drug kits.
- Study drug and diary training.
- Study drug administration under supervision of study staff and observation for at least 1 hour thereafter.
- AEs and concomitant medications.

14.7 Open Label Extension Weeks 40 and 44 Procedures/Assessments

- Investigator administered ALSFRS-R.
- C-SSRS.
- Limited physical examination.
- Weight.
- Vital signs.
- Clinical laboratory tests.
- Urine pregnancy.
- Study drug accountability.
- Contact IXRS and dispense study drug kits.
- AEs and concomitant medications.

14.8 Open Label Extension Weeks 48 and 72 Procedures/Assessments

- █
- █
- █

- C-SSRS.
- Investigator administered ALSFRS-R.
- [REDACTED]
- Limited physical examination.
- Weight.
- Vital signs.
- Spirometry.
- Clinical laboratory tests.
- Lipid panel.
- HbA1c.
- Urine pregnancy.
- Study drug accountability.
- Contact IXRS and dispense study drug kits.
- AEs and concomitant medications.

14.9 Open Label Extension Week 60 Procedures/Assessments

- [REDACTED]
- [REDACTED]
- [REDACTED]
- C-SSRS.
- Investigator administered ALSFRS-R.
- [REDACTED]
- Limited physical examination.
- Weight.
- Vital signs.
- Spirometry.
- [REDACTED]
- Clinical laboratory tests.
- Lipid panel.

- HbA1c.
- Urine pregnancy.
- Study drug accountability.
- Contact IXRS and dispense study drug kits.
- AEs and concomitant medications.

14.10 Open Label Extension Week 84/ Early Termination

Procedures/Assessments

- [REDACTED]
- [REDACTED]
- [REDACTED]
- C-SSRS.
- Investigator administered ALSFRS-R.
- [REDACTED]
- Complete physical examination.
- Weight.
- Vital signs.
- Spirometry.
- [REDACTED]
- Clinical laboratory tests.
- Lipid panel.
- HbA1c.
- Serum pregnancy.
- Study drug accountability.
- Contact IXRS and dispense study drug kits.
- AEs and concomitant medications.

Subjects who early terminate from the Open Label Extension for any reason must undergo the taper of study drug (2x/week for 2 weeks followed by 1x/week for 1 week) and should complete the End of Taper and Follow-up Visits.

14.11 Week 39 or Week 87/End of Taper Procedures/Assessments

At Week 39 (+ 5 days) or Week 87 (+ 5 days) the subject will be contacted via telephone and the following assessments will be made:

- AEs and concomitant medications.

14.12 Follow-up Visit Procedures/Assessments

The following procedures will be completed at the follow-up visit 28 (\pm 2) days after the final dose of study drug:

- Telephone administered ALSFRS-R (not required for the Open Label Extension Follow-up Visit).
- Investigator administered ALSFRS-R.
- Current medical condition review.
- Limited physical examination.
- Weight.
- Vital signs.
- Spirometry.
- Clinical laboratory tests.
- Urine pregnancy test.
- Subject diary review.
- Study drug accountability.
- AEs and concomitant medications.

14.13 Unscheduled Visit Procedures/Assessments

Any time that an unscheduled visit is needed during the Randomized Treatment Period to assess the subject for the study (for example, for an AE), the following minimum evaluations must be completed:

- Telephone administered ALSFRS-R.
- Current medical condition review.
- Limited physical examination.
- Weight.

- Vital signs.
- AEs and concomitant medications.

15 INVESTIGATIONAL MEDICINAL PRODUCT (Study Drug)

15.1 Methods of Assigning Subjects to Treatment Groups

15.1.1 Randomization and Stratification

Subjects will be randomized according to a computer-generated allocation scheme to receive either Acthar 0.2 mL (16 U) or placebo 0.2 mL. Both investigators and the subjects will be blinded to the treatment assignment. The randomization will be stratified for riluzole use (yes/no) and the predicted values of the 9-month decline rate of ALSFRS score from baseline (≤ 1 point change/month vs > 1 point change/month) generated from the prize winning algorithm of the DREAM Phil Bowen ALS Prediction Prize4Life Challenge ([Küffner et al, 2015](#)).

In the Randomized Treatment Period, for each stratum, a separate randomization scheme will be produced. A block randomization will be performed. Subjects will not be randomized in the Open Label Extension Period. The biostatistician will decide on the details at the time of the creation of the randomization scheme.

The DREAM Phil Bowen ALS Prize4Life Challenge was issued to promulgate development of algorithms that could predict disease progression in ALS. The algorithm developers were provided with a small subset of data from the PRO-ACT database that included 3 months of individual patient level clinical trial information that was to be used to predict disease progression over the subsequent 9 months. There were 37 algorithm submissions, and each algorithm was then evaluated on a separate data set from the PRO-ACT database. The 2 winning algorithms both predicted disease progression better than a baseline model and clinicians using the same data.

Mallinckrodt contacted the developers of 1 of the prize winning algorithms in order to apply the algorithm to stratify the subjects in a previous trial (QSC01-ALS-01, [Mallinckrodt, 2016a](#)). The algorithm was modified to only use the available variables as predictors, which were collected from subjects' Screening Visit. The algorithm was validated with a subset of PRO-ACT data, and the root mean square error of the validation is 0.517, which is very close to the original algorithm. In this study, the ALSFRS-R score collected at the Baseline Visit will be converted to ALSFRS score by dropping the last 2 questions (Questions 11 and 12) since most of the records in PRO-ACT database use ALSFRS scoring system.

The algorithm will be implemented after the Screening Visit, and a 9-month decline rate in ALSFRS score will be generated based on the screening and baseline data, which will be used to stratify the subjects when they return for the Baseline Visit.

15.2 Interactive Phone/Web Response System

The investigator or designee will contact IXRS to register subjects at screening. The subject's identification (ID) number will be determined by the IXRS and will be used to identify the subjects for the duration of the study within all systems and documentation. Subject identification numbers will consist of 7 digits: the first 4 digits reflect the site number assigned to the investigator and the last 3 digits are the subject number.

A subject ID number will not be assigned to more than 1 subject. If a subject is not eligible to receive treatment, or should a subject discontinue from the study, the subject ID number cannot be reassigned to another subject.

In the event that a subject is rescreened within the screening window, they do not need a new subject ID number. At Baseline, qualified subjects who meet all of the eligibility criteria will be enrolled into the study.

The investigator or designee must contact the IXRS to report subjects as a screen failure if the subject does not meet eligibility criteria predose.

The investigator or designee must contact IXRS to record each subject visit, to receive the study drug kit assignments, and to report any subject status changes.

The investigator must maintain a subject master log linking the subject ID to the subject's name. The investigator must follow all applicable privacy laws in order to protect a subject's privacy and confidentiality. Information that could identify a subject will be masked on material received by the sponsor.

15.3 Emergency Identification of Investigational Medicinal Product

In case of an emergency during the Randomized Treatment Period, when knowledge of the investigational product assignment is required for the medical management of an individual subject, the investigator may obtain the treatment assignment of the subject experiencing the emergency. The treatment blind for that subject may be broken by accessing the IXRS using instructions provided. The investigator must notify the sponsor's MM or physician designee immediately after determining that it is necessary to unblind the treatment assignment. The investigator and sponsor should make every effort to document and limit the people who are

unblinded to the subject's treatment assignment. The investigator must also indicate in source documents that the blind was broken and provide the date and reason for breaking the blind.

15.4 Dosing Procedures

Both Acthar (80 U/mL) and the placebo are supplied as 5 mL multidose vials. The vials should not be over pressurized prior to withdrawing the product. The vials should be warmed to room temperature before using and will be labeled according to all applicable national and local regulations.

The following treatments will be administered:

Randomized Treatment Period

- Treatment A: Acthar 0.2 mL (16 U) SC QD for 36 weeks. Subjects who do not enter the open label extension will then taper with Acthar 0.2 mL (16 U) administered 2x/week for 2 weeks, then 1x/week for 1 week.

OR

- Treatment B: Placebo 0.2 mL SC QD for 36 weeks. Subjects who do not enter the open label extension will then taper with placebo 0.2 mL administered 2x/week for 2 weeks, then 1x/week for 1 week.

Open Label Extension:

- Acthar 0.2 mL (16 U) SC QD for 48 weeks, followed by Acthar 0.2 mL (16 U) administered 2x/week for 2 weeks, then 1x/week for 1 week.

The subject or subject's caregiver will administer the first dose of study drug and the first dose of Acthar in the Open Label Extension in the clinic under the supervision of study staff. The subject will remain in the clinic for at least 1 hour postdose to monitor for allergic or anaphylactic reactions. All other doses will be administered by the subject or the subject's caregiver at home.

15.4.1 Treatment Discontinuation

Subjects who early terminate for any reason must undergo the taper (2x/week for 2 weeks followed by 1x/week for 1 week) and should complete the End of Taper and Follow-up Visits.

Subjects who early terminate from the Randomized Treatment Period for any reason other than withdrawal of consent should be encouraged to continue minimal study participation via

telephone contact on a monthly basis if possible. In this circumstance, the ALSFRS-R should be administered over the telephone by the site, and any status update should be collected.

Treatment with study drug should be discontinued if any of the following occur:

- Development of accelerated hypertension (defined as systolic blood pressure ≥ 180 and diastolic blood pressure ≥ 100 mm Hg) that cannot be managed by the adjustment of concomitant medications such as antihypertensive medications.
- Development of congestive heart failure that cannot be managed by the adjustment of concomitant medications such as diuretics and antihypertensive medications.
- Development of diabetic signs/symptoms (ie, HbA1c $> 6.5\%$, or fasting plasma glucose > 126 mg/dL, or classic symptoms of hyperglycemia with random plasma glucose > 200 mg/dL) that cannot be managed by the adjustment of concomitant medications such as insulin and oral hypoglycemic agents.
- MedDRA System Organ Class infection/infestation of \geq moderate intensity.
- Hy's Law cases (ALT > 3 x ULN, with total bilirubin > 2 x ULN, no initial signs of cholestasis [alkaline phosphatase within the reference range]), and no other reason can be found to explain liver injury).

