- All female subjects of child-bearing potential will have a serum pregnancy test at the Screening and Week 36/End of Study Visits. Urine pregnancy tests will be done at all other visits throughout the study. Results must be available prior to dosing with protocol mandated study drug. Subjects with positive results will be ineligible for study entry (Screening Visit or Predose) or withdrawn from the study. Any female subject that becomes pregnant during the study will be immediately withdrawn and the pregnancy report as per [Section 21.5](#).

If applicable, the subject's agreement to use contraception throughout their study participation (through the Follow-up Visit) will be documented.

- Lipid panels will be done at specified times during the study. The lipid panel will include total cholesterol, low density lipoprotein (LDL), high density lipoprotein (HDL), and triglycerides.
- HBsAg and HBcAb will be performed at the Screening Visit. Results of these tests must be negative or nonreactive for subjects to qualify for the study.
- HCV will be performed at the Screening Visit. A positive HCV will automatically trigger a HCV PCR analysis. HCV PCR must be < 25 IU/mL to qualify for the study.
- IGRA for TB will be performed at the Screening Visit. Results of this test must be negative for subjects to qualify for the study.
- HbA1c will be performed at the Screening Visit HbA1c must be $\leq 6.5\%$ for subjects to qualify for the study. Additional HbA1c tests will be done at specified times during the study.

- [REDACTED]

Out-of-Range Laboratory Values

[figure not shown]
[figure not shown]
Laboratory values from samples collected at the Screening Visit will be evaluated by the investigator for eligibility of the subject in the study. Clinical laboratory tests may be repeated once to determine subject eligibility.

[figure not shown]
Laboratory values that fall outside the reference range from samples collected during the study or at study exit or early termination will be assessed by the investigator for clinical significance. If the out of range value for samples is deemed clinically significant by the investigator, an AE will be recorded.

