21.5 Pregnancy Reporting

Certain information, although not considered an SAE, must be recorded, reported, and followed up as indicated. This includes the following:

Pregnancy exposure to an investigational medicinal product, except for exposure to prenatal vitamins. Subjects should not become pregnant during the study. If the subject becomes pregnant, study treatment must be discontinued immediately. The investigator must report the pregnancy by submitting the appropriate form to Mallinckrodt Global Pharmacovigilance or designee within 24 hours of confirmation of a pregnancy (ie, positive serum pregnancy test

result). The outcome of pregnancy (eg, spontaneous abortion, live birth, still birth, congenital anomalies, birth defects) must be reported by submitting the appropriate form to Mallinckrodt Global Pharmacovigilance or designee within 24 hours of the pregnancy outcome being submitted to the study site. If the pregnancy results in a live birth, a postdelivery follow-up will be performed at least 28 days after the baby is born and must be reported to Mallinckrodt Global Pharmacovigilance or designee within 24 hours of the study site becoming aware of the follow-up information. Both maternal and paternal investigational medicinal product exposures are collected.

If the female partner of a male subject becomes pregnant during the study, the site will forward the Pregnancy Notification Form and the Pregnancy Report Fax cover page to Mallinckrodt Global Pharmacovigilance or designee, within 24 hours of being notified. The outcome of pregnancy (eg, spontaneous abortion, live birth, still birth, congenital anomalies, birth defects) must be reported by submitting the appropriate form to Mallinckrodt Global Pharmacovigilance or designee within 24 hours of the pregnancy outcome being submitted to the study site. If the pregnancy results in a live birth, a postdelivery follow-up will be performed at least 28 days after the baby is born and must be reported to Mallinckrodt Global Pharmacovigilance or designee within 24 hours of the study site becoming aware of the follow-up information.

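### The taper is compulsory after every early termination, but pregnancy requires study treatment to stop immediately; the protocol does not say which rule governs

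*Combined protocol and SAP*

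**What the plan says.** The taper rule appears four times, each time without an exception. Section 15.4.1 reads "Subjects who early terminate for any reason must undergo the taper (2x/week for 2 weeks followed by 1x/week for 1 week"), and Table 7-1 footnote a says the same. Section 14.5 has "Subjects who early terminate from the Randomized Treatment Period for any reason must undergo the taper of study drug", and 14.10 has "Subjects who early terminate from the Open Label Extension for any reason must undergo the taper of study drug". Section 15.4 shows what the taper contains: injections of the same 0.2 mL volume (16 U for Acthar) at a reduced frequency.

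The pregnancy rule is in 21.5: "If the subject becomes pregnant, study treatment must be discontinued immediately". It does not mention the taper. Section 18.8 says of pregnancy tests "Results must be available prior to dosing with protocol mandated study drug" and "Subjects with positive results will be ineligible for study entry (Screening Visit or Predose) or withdrawn from the study", and adds that a subject who becomes pregnant on study is withdrawn at once. Section 22.1 gives a positive pregnancy test as an example under its withdrawal criteria. It also says that withdrawn subjects have the Early Termination and Follow-up assessments, without mentioning the taper.

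**The concern.** A subject withdrawn for pregnancy is a subject who terminates early. Under 15.4.1 she must be given the taper; under 21.5 her study treatment must stop immediately. Both are worded as obligations, and neither section refers to the other. Pregnancy is also absent from the list of discontinuation reasons in 15.4.1.

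At stake is whether a pregnant subject receives further study drug, which would depend on the section the site happens to follow. Sites could act differently under the same protocol, and a site following 15.4.1 to the letter would breach 21.5. The date of the Follow-up Visit, which is timed from the last dose, would differ too.

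**Working it through.** The plan states no figure on this point, so the check compares the sections and then counts what separates the two readings.

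**Do both rules reach the same subject?**

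| Step | Source | Reading |
|---|---|---|
| Pregnancy leads to withdrawal | 18.8, 22.1 | The subject terminates early |
| Early termination leads to the taper | 15.4.1, Table 7-1 footnote a, 14.5, 14.10 | Further study drug is required |
| Pregnancy leads to an immediate stop | 21.5 | Continued dosing is not allowed on a literal reading |
| Order of precedence | None | Not stated |

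The case can arise in a single visit: 14.5 lists both the serum pregnancy test and the dispensing of taper kits at Early Termination. Under 18.8 every laboratory test except the urine pregnancy test goes to a central laboratory. Subjects who complete Week 36 taper under 15.4 and are not part of this example.

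**Is the taper rule literally universal?** It cannot be, because 22.1 also lists death and loss to follow-up as reasons for discontinuation. The rule therefore has unwritten limits, and no section says whether pregnancy is one of them.

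**Could discontinuation include the taper?** Section 11.2 times the follow-up visit at 28 days after study drug is discontinued. Its totals are:

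- without the extension: 4 + 36 + 3 + 4 = 47 weeks
- with the extension: 4 + 36 + 48 + 3 + 4 = 95 weeks

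Both match the stated durations only if the 28 days begin after the 3-week taper, so in 11.2 discontinuation comes after the taper and does not contain it.

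**Doses per affected subject** (assuming the early-termination taper uses the 15.4 dose)

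- Number of doses: 2 × 2 + 1 × 1 = 5
- Acthar: 5 × 16 U = 80 U
- Placebo: 5 × 0.2 mL = 1.0 mL
- Under a literal reading of 21.5: 0

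**Follow-up Visit.** Let Day 0 be the last daily dose, and assume the taper starts the next day; the protocol does not give this timing. The single dose of taper week 3 then falls on Day 15 to 21.

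- With the taper: 15 + 28 = Day 43 to 21 + 28 = Day 49 (Day 41 to 51 with the ± 2 day window)
- Without the taper: Day 28 (Day 26 to 30 with the window)
- Nominal shift: 43 − 28 = 15 to 49 − 28 = 21 days

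**Adverse event recording.** Section 21.4 gives two end points. If recording ends at the Follow-up Visit it shifts by the same 15 to 21 days; if it ends at the Early Termination visit it does not shift. Pregnancy outcome reporting under 21.5 continues either way: "If the pregnancy results in a live birth, a postdelivery follow-up will be performed at least 28 days after the baby is born".

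**The case against.** The strongest reply is that other sections already settle the matter. Section 18.8 requires a pregnancy result before dosing, and taper injections are dosing. Section 21.5 is specific to pregnancy, whereas 15.4.1 is general, and specific rules normally override general ones. Section 22.1 sends withdrawn subjects to follow-up with no mention of the taper. On this view only a cross-reference is missing.

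That does not dispose of the point. The consequence 18.8 attaches to a positive test is withdrawal, and withdrawal is what triggers the taper rule, so the argument is circular. The protocol nowhere says that specific rules override general ones, and the taper rule is written in universal terms four times. Silence in 22.1 neither applies nor waives the taper.

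One could also argue that discontinuation includes the taper, because 15.4.1 is headed Treatment Discontinuation and contains it, while 11.2 is only a planning sum for subjects who complete treatment. That reading is possible and 11.2 does not rule it out, but no section adopts it, and the immediacy required in 21.5 and 18.8 tells against it.

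Several limits do stand. Contraception is required through follow-up (12.1), testing is frequent, 9.1 puts typical onset in the 5th or 6th decade, and pregnancies are reported to the sponsor within 24 hours of confirmation. A later Follow-up Visit is not a harm in itself, since it is due 28 (± 2) days after the final dose either way. The two end points in 21.4 are a separate inconsistency that exists without any pregnancy. What matters most is five doses against none.

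**Conclusion.** The concern holds. Two compulsory instructions apply to a subject who becomes pregnant on study, they cannot both be followed as written, and precedence is not stated. The difference is 5 doses (80 U of Acthar or 1.0 mL of placebo) against 0 per affected subject, assuming the 15.4 dose. The 15 to 21 day shift of the Follow-up Visit is secondary and also assumes that the taper starts the day after the last daily dose.

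The reach is narrow: the documents give no expected number of pregnancies, and there may be none. No effect on the primary analysis, power or sample size is claimed. It should still be corrected, because it decides whether a pregnant subject is given more study drug.

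**What to change.** Reconcile 15.4.1, Table 7-1 footnote a, 14.5 and 14.10 with 18.8, 21.5 and 22.1. State in one place how the taper rule applies when immediate discontinuation is required, and cross-refer to that statement from the other sections. This review takes no position on which rule is right; that decision belongs to the sponsor's medical team.

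The cost is one clarifying clause with cross-references in the next amendment and a memo to sites. Neither the analysis nor the sample size changes.
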